### **4.2.2 Neurodevelopment assessments**

For the neurodevelopment assessments, the following study-related duties are assigned to NeuroCog Trials Holdings, Inc., [name]: development of a study-specific assessment manual, study-specific training and certification of local child-development assessors, central data quality assurance of completed assessment forms, calculation of final scores and determination of Age Equivalence scores, and data management.

The development of the study-specific manual will be in collaboration with Shapiro Neuropsychology Consulting LLC, [name]

#### **4.4 Central MRI reading**

████████████████████ is assigned to develop a study-specific MRI manual applicable for the MRI scans to be used at study sites, validation of test-data from each site, quality assurance of completed MRI scans, and determination of the brain and abdominal variables from completed MRI assessments, as specified in Section 7.5.3.3.

#### **4.5 Data monitoring committee**

A data monitoring committee (DMC), independent from Sobi and Principal Investigators, is assigned to monitor all safety and immunogenicity data at intervals specified in Section 7.5.4.8. The primary responsibility of the DMC is to provide safety oversight of the study conduct in order to protect study participants.

The DMC employed in the FIH study ([SOBI003-001](#)) will continue to monitor safety and immunogenicity data in this extension study.

The DMC is planned to comprise an independent statistician and 2 clinicians that, collectively, have experience from DMC, management of pediatric patients with lysosomal storage disease (LSD), clinical immunology, and the conduct of clinical studies with enzyme replacement therapy (ERT).

A DMC charter will outline DMC membership, responsibilities, data review meeting details, and lines of communication with the study teams at Sobi and INC Research.

## **5 Introduction**

Sobi is developing SOBI003, a chemically modified recombinant human sulfamidase, for enzyme replacement in patients with Mucopolysaccharidosis type IIIA (MPS IIIA); Sanfilippo A syndrome. MPS IIIA is a rare disease with rapid progression from early childhood, often resulting in death during the 2nd or 3rd decade of life. Currently there is no approved treatment and to date, therapy is limited to treatment and relief of symptoms. The unmet medical need is therefore high.

This extension study SOBI003-002 is designed to assess the safety and tolerability of long-term SOBI003 treatment and to evaluate the efficacy of SOBI003 in improving neurocognitive function and other measures indicative of a favorable outcome of SOBI003 treatment as compared to untreated MPS IIIA patients.

Patients completing the 24-week, open-label treatment period of the FIH study (SOBI003-001) with SOBI003 will be offered enrolment into this extension study. The current study will be a direct continuation of the FIH study (SOBI003-001), thus commencing with Week 25 and ending at Week 104, giving a total SOBI003 treatment duration of 2 years.

## 5.1 Background

### 5.1.1 MPS IIIA

MPS IIIA or Sanfilippo A, is an inherited LSD that is progressive, life-shortening and rare. MPS IIIA is one of 4 distinct subtypes of MPS III (denoted IIIA, IIIB, IIIC and IIID) (3).

MPS IIIA is an autosomal recessive disorder caused by mutations in the *SGSH* gene that result in absence of or a deficiency in the enzyme sulfamidase (N-sulfoglucosamine sulfohydrolase). Lack of sulfamidase activity leads to insufficient degradation of HS and lysosomal accumulation of HS and its metabolites in lysosomes throughout the body (4). As of today, 142 mutations have been described in the *SGSH* gene coding for sulfamidase (5). Data suggest a geno- and phenotype correlation and that patients homozygous or compound heterozygous for the S298P mutation have a slower progression of the disease (6).

Depending on disease severity, patients have a median life-expectancy of about 15 years. The clinical course of MPS IIIA can be divided into 3 phases (7). In the first phase, which usually starts between 1 and 4 years of age, a developmental delay becomes apparent after an initial normal development during the first 1 to 2 years of life. The most prominent finding in this phase is speech delay (6, 7, 8).

The diagnosis of MPS IIIA is usually established during the second phase, which generally starts around 3 to 4 years of age. This phase is characterized by increasing behavioral problems with hyperactivity, aggressive and destructive behavior as well as reduced attention span (7), which responds poorly to standard medications and behavioral-based interventions (9). A pronounced and rapid decline in cognitive skills becomes evident and the sleeping pattern is disturbed with extreme difficulty in falling asleep and with frequent awakening (10).

In the third and final “quiet” phase, behavioral symptoms diminish while motor retardation emerges with walking and swallowing difficulties sometimes requiring percutaneous endoscopic gastrostomy (PEG) feeding. The progressive neurodegeneration causes spasticity, seizures, loss of speech, and severe dementia, which ultimately results in a vegetative state (9).

Patients usually die from respiratory infections in the end of the second or beginning of the third decade of life (11) although patients with a slowly progressing phenotype may live longer (6).

### 5.1.2 SOBI003

SOBI003 is a chemically modified variant of recombinant human sulfamidase. SOBI003 is a sterile solution for i.v. infusion after dilution. In this extension study, SOBI003 is administered once weekly.

By modification of the sulfamidase glycans, the uptake of SOBI003 systemically is strongly reduced. This translates into a reduced serum clearance as demonstrated in mice. SOBI003 passes the blood-brain barrier (BBB) presumably by passive transcytosis, whereby the increased plasma exposure facilitates generation of pharmacological relevant levels of SOBI003 in the central nervous system (CNS) compartment. Once SOBI003 enters the target cells and reaches the lysosomal compartment, it shows enzymatic activity and stability comparable to that of unmodified sulfamidase, as demonstrated in fibroblasts of MPS IIIA patients.

### 5.1.3 SOBI003 nonclinical development

In a MPS IIIA mouse model with a spontaneous missense mutation of the *SGSH* gene, disease manifestations similar to the human conditions are obtained, including lysosomal storage of HS and neurological pathology. In these mice, repeated i.v. administration of SOBI003 resulted in a dose and time dependent clearance of HS in brain. The reduction in HS translated into improvements in terms of lysosomal size and neuroinflammation as well as beneficial effects on behavioral impairments.

HS reduction in cerebrospinal fluid (CSF) correlated with reduction of HS in whole brain of MPS IIIA mice following repeated i.v. administration of SOBI003, thus supporting the use of HS reduction in CSF as a biomarker of disease modification.

In MPS IIIA mice, a relationship between treatment effect and SOBI003 dose level and treatment duration was observed. The reduction of HS in brain was related to the accumulated active SOBI003 dose. The return to baseline HS biomarker levels after discontinuation of treatment was also a gradual process in this mouse model. To quantify and understand the dose, time, concentration and effect relationship in MPS IIIA mice, a semi-mechanistic in silico model was developed based on mouse PK, distribution of SOBI003 to the brain, SOBI003 entering target cells, the intracellular retention of SOBI003 and an intracellular SOBI003 concentration-effect relationship on HS reduction. Human fibroblasts of an MPS IIIA patient (27) were used for in vitro determination of SOBI003 cell entry rate, cell retention, and intracellular concentration-effect relationship. Allometric scaling from rat and cynomolgus monkey to human was applied to predict clearance and volume of distribution in patients (body weight 20 kg). Translating the mouse in silico model to human repeated weekly administration of 3 mg/kg, SOBI003 is predicted to gradually achieve a brain HS reduction of ~ 35 % after 3 months and ~ 45 % after 6 months treatment. Thus, according to model-based simulations using the in silico model, the 3 mg/kg dose level is expected to gradually elicit a pharmacological effect in CNS in humans. Repeated weekly administration of 10 and 20 mg/kg SOBI003 is predicted to achieve a brain HS reduction of ~ 75 % and ~ 80 % after 3 months and ~ 80 % and ~ 85 % respectively after 6 months treatment relative to baseline.

Nonclinical safety assessments have been performed to support the SOBI003 development program. The nonclinical safety studies were performed in accordance to international standards for drug development and OECD Principles of GLP. A 3-month toxicity study was performed in MPS IIIA mice, a disease model to evaluate any potential interactions of the drug and the disease. A 1-month toxicity study in healthy non-human primates (cynomolgus monkey) was also performed. In addition, to support the clinical development in pediatric patients, juvenile rats were treated for one month from 10 days up to 5 weeks of age, which corresponds to a life-span in humans ranging from neonates up to the age of 6 years. Throughout the nonclinical safety program SOBI003 was administered by i.v. infusion every third day following pre-treatment with anti-histamine to appropriately resemble the clinical treatment regimen.

In the species tested, the treated animals did not show any signs of adverse effects. Thus, the safety evaluation of SOBI003 has shown that it is well-tolerated. In favor of SOBI003 treatment was also improvements in the disease state in MPS IIIA mice, such as lower incidences and/or severity of microscopic findings and with lower kidney, liver and spleen weights. However, the histopathological examinations revealed that the treatment of all three species at higher doses were associated with an accumulation of eosinophilic material in the cytoplasm of macrophages of various origin; liver, lymph nodes and the heart. The observations were clearly dose dependent and did not cause any detected harmful effects or other negative consequences to the animals. The observations were partially reversible after 4 weeks withdrawal of treatment. The anomalies were judged to be a result of a normal physiological function of tissue macrophages to scavenge proteins and the observed accumulation may be due to the high protein load. Thus, since these findings were not considered as adverse the NOAEL was set to the highest dose administered in the three species tested, i.e., 300 mg/kg in the mice and rats and 150 mg/kg in the cynomolgus monkeys.

The lowest SOBI003 serum exposures at the NOAEL dose levels in these species were observed in the mice following the 300 mg/kg dose, where mean  $C_{max,ss}$  was 86.3 and 163  $\mu\text{mol/L}$  and mean  $AUC_{\tau,ss}$  was 718 and 934  $\mu\text{mol}\cdot\text{h/L}$  in in male and female mice, respectively. Based on predicted steady state PK in patients ( $C_{max,ss}$  0.89, 3.0, and 5.9  $\mu\text{mol/L}$ ;  $AUC_{\tau,ss}$  11.5, 38.5, and 77.0  $\text{h}\cdot\mu\text{mol/L}$  at dose levels 3, 10 and 20 mg/kg), the margins to SOBI003 exposure in the pivotal toxicity studies are thus at least 100-fold for a starting dose of 3 mg/kg and at least 10-fold for a dose of 20 mg/kg. Further details are presented in the SOBI003 [Investigator Brochure](#)).

#### **5.1.4 SOBI003 immune mediated reactions**

In an initial explorative study in MPS IIIA mice, where the efficacy of 3 different sulfamidase derivatives was assessed (whereof SOBI003 was one), Sobi encountered hypersensitivity reactions. Mice were given the test articles at 30 mg/kg every other day as a bolus injection without antihistamine pretreatment. The study was terminated due to hypersensitivity reactions in connection with the fifth i.v. dose. A second study was performed, where the mice were pretreated with the antihistamine chlorpheniramine, and the injection rate was extended to approximately 5 to 10 seconds per injection. The same test articles, doses, and dose frequencies were applied as in the initial study, and the second study could be finalized as planned without

any abnormal observations (a 25-day treatment period with a total of 13 injections). Subsequently, antihistamine pretreatment was included in the chronic efficacy studies.

The nonclinical studies in MPS IIIA mice show that ADAs are generated against SOBI003. In the studies performed with anti-histamine pretreatment, including the 3 month toxicity study the ADA response does not compromise safety or alter the exposure, as assessed at 24 hours after last dose administration. A number of chronic efficacy studies have been performed with antihistamine pretreatment in MPS IIIA mice without observing any obvious toxicities or lack of efficacy. In cynomolgus monkey a repeated dose paradigm with doses once every third day indicated that ADAs had an impact on SOBI003 exposure. ADAs did not appear to impact the  $C_{max}$  in plasma, but possibly the AUC. Apart from these deviations, exposure after the last dose was similar to that observed after the first dose. No ADA development was seen in the pivotal juvenile rat toxicity study.

Development of ADAs is a common finding in ERTs and correlates to the degree of endogenous enzyme expression (12, 13, 14, 15). Nonclinical assessments of immunogenicity of human proteins, applying *in silico*, *in vitro*, or animal models have, so far, shown only limited or no translatability to the clinical situation.

The polypeptide sequence of SOBI003 is identical to human sulfamidase. However, as a result of use of the CHO expression system and the glycan modifications, through which some peripheral carbohydrate ring structures in the glycans are linearized, the overall structure of SOBI003 is not identical to human sulfamidase. Therefore, an immune reaction to SOBI003 may be expected in analogy to what occurs with other ERTs. ADAs and their impact on safety, PK and PD are monitored closely in this extension study.

### 5.1.5 Study rationale

SOBI003 is being developed for treatment of MPS IIIA. Scientific advice on the nonclinical and chemistry, manufacturing and control (CMC) development has been obtained from the FDA on 16 February 2016 and from EMA in 28 June 2016. A pre-IND meeting was held with the FDA on 21 June 2017 to obtain agreement on the conduct of the FIH study ([SOBI003-001](#)) with SOBI003.

The FIH study ([SOBI003-001](#)) is designed to assess the safety, tolerability, PK, PD and immunogenicity of SOBI003 at 3 dose levels to provide knowledge needed to optimize the further evaluation of SOBI003 in patients with MPS IIIA. Patients completing the 24-week, open-label treatment period of the FIH study will be offered enrolment into the extension study SOBI003-002.

Study SOBI003-002 is designed to assess the safety and tolerability of long-term SOBI003 treatment and to evaluate the efficacy of SOBI003 in improving neurocognitive function and other measures indicative of a favorable outcome of SOBI003 treatment. The follow-up period of the extension study is 80 weeks, giving a total SOBI003 treatment duration of 104 weeks to allow for a comparison with data from a recent NH study (22).

## 5.2 Potential risks and benefits

MPS IIIA is an irreversible, progressive, life-shortening disease with no existing effective therapeutic alternative. SOBI003 provides a potential clinical benefit by reducing the levels of stored HS and its metabolites, and thereby reducing neuro-inflammation and the clinical manifestations of MPS IIIA.

Apart from ADA development in two species (MPS IIIA mouse and cynomolgus monkey) out of the three included in the pivotal toxicity program, which is an expected finding considering the foreignness of a human protein to animal species, the nonclinical safety evaluation of SOBI003 did not show any signs of adverse effects, thus SOBI003 was well-tolerated.

Given the observed pharmacological and toxicology profile in non-clinical studies, and following patient completion of 24 weeks treatment in the FIH study ([SOBI003-001](#)), it is judged that SOBI003 can be given to patients in a carefully monitored extension study. Adherence to study inclusion/exclusion criteria and close clinical monitoring will be applied.

Although SOBI003 has been given for 24 weeks in the 001-study, hypersensitivity reactions/immune-mediated adverse reactions may still occur, including anaphylaxis and infusion reactions, are commonly reported for lysosomal ERTs. To reduce the incidence and severity of these adverse reactions, slow infusion rates, prolonged infusion duration and pretreatment with antihistamines will be applied. Severe and potentially life-threatening adverse hypersensitivity/immune-mediated reactions may, however, still occur.

Close clinical supervision by medical staff that are experienced with ERT treatment will be applied during and after the infusions. This will ensure early detection and adequate treatment of potential adverse reactions. Potential hypersensitivity reactions including anaphylactic events and infusion related reactions will be treated in accordance with the current anaphylactic algorithm (17). Further symptomatic treatment with antipyretics and additional antihistamines may be administered to manage milder hypersensitivity/immune-mediated reactions. Immunosuppressant treatment will be administered in cases of less tolerable reactions. In addition, the availability of cardiopulmonary resuscitation equipment and immediate access to emergency medical services is secured.

Potential delayed hypersensitivity reactions may occur outside the hospital setting (refer to Table 1) for minimum hospitalization periods during study participation). Parents/caregivers will be carefully informed of potential signs and symptoms of delayed hypersensitivity reactions and of the importance to seek immediate medical attention.

SOBI003 has the potential to become the first disease modifying therapy in patients with MPS IIIA. The disease-modifying effect of SOBI003 is believed to be most beneficial if treatment is started in very young patients since they have limited neuronal damage. SOBI003 could possibly stop, or reverse, the progress of the neuronal damage and the neurocognitive decline leading to a normal or a near normal neurocognitive development. In older patients, that have more pronounced neuronal damage, it is likely that already developed neuronal damage is not reversible. However, further disease progression might be prevented or at least slowed down.

The ultimate effect of the disease modifying effect would be to improve the cognition and thereby prolong life, minimize behavioral problems and sleep disturbances, and increase QoL including reduction of caregiver burden. The evaluation of the benefits of SOBI003 treatment in pediatric patients with MPS IIIA is based on the results in the SOBI003 non-clinical studies showing reduced levels of stored HS and its metabolites in brain and CSF, reduction of neuroinflammation in brain, reduction of lysosomal swelling and secondary storage products in brain as well as trends towards a beneficial effect on behavioral impairment. If translated to human these beneficial effects may reduce the devastating clinical manifestations of MPS IIIA.

Potential study procedural risks include the use of sedation/general anesthesia and use of a central venous access port. To minimize study related procedural risks, local hospital routines will be applied for the procedures. The selection of anesthetic method will be in accordance with local hospital routines and as judged by pediatric anesthesiologist with prior experience from MPS patients. The parents/caregivers will be trained in management of the port, in accordance with local hospital routines. This includes the actions to take in case an infection is suspected. The central venous access port is added as part of the preceding FIH study ([SOBI003-001](#)), but there may be occasions when a patient may need to replace an existing port.

In summary, the potential benefits of SOBI003 treatment are considered to outweigh the foreseeable risks.

## **6 Study objectives and endpoints**

The efficacy analysis will be based on data 2 years after the start of the FIH study ([SOBI003-001](#)), baseline being baseline assessments in the FIH study.

### **6.1 Primary objective**

The primary objective is:

- To assess the long-term safety and tolerability of SOBI003

#### **6.1.1 Primary endpoint**

The primary endpoint to evaluate the safety and tolerability of SOBI003 is:

- Treatment Emergent Adverse Events (TEAEs) and Serious Adverse Events (SAEs)

#### **6.1.2 Secondary endpoints related to the primary objective**

The secondary endpoints to evaluate the safety and tolerability of SOBI003 are:

- Vital signs (blood pressure, heart rate, body temperature, respiratory rate and oxygen saturation)

- Laboratory safety variables (hematology, coagulation, clinical chemistry and urine analysis)

## 6.2 Key secondary objectives

- To evaluate the efficacy of SOBI003 on neurocognitive function, as compared to untreated MPS IIIA patients from a NH control
- To evaluate the effect of SOBI003 on HS levels in CSF

### 6.2.1 Key secondary endpoints

The endpoints relating to the key secondary objective are:

Study efficacy evaluation will primarily be based on:

- Change from baseline at Week 104 in Development Quotient (DQ) as assessed by the Bayley Scales of Infant and Toddler Development®, third edition (BSID-III) cognitive subtest or the Kaufman Assessment Battery for Children, Second edition (KABC-II)
- Change from baseline at Week 104 in CSF HS

Additional key secondary endpoints are:

- Change from baseline at Week 52 in Development Quotient (DQ) as assessed by the Bayley Scales of Infant and Toddler Development®, third edition (BSID-III) cognitive subtest or the Kaufman Assessment Battery for Children, Second edition (KABC-II)
- Change from baseline at Weeks 52 and 104 in Age Equivalent (AEq) as assessed by the Bayley Scales of Infant and Toddler Development®, third edition (BSID-III) cognitive subtest or the Kaufman Assessment Battery for Children, Second edition (KABC-II)
- Change from baseline at Week 52 in CSF HS

## 6.3 Secondary objectives

The secondary objectives are:

1. To assess the effect of SOBI003 on adaptive behavior, as compared to untreated MPS IIIA patients from a NH control
2. To assess the effect of SOBI003 on HS levels in serum and urine
3. To assess the effect of SOBI003 on brain magnetic resonance imaging (MRI) abnormalities
4. To assess the effect of SOBI003 on liver and spleen volume
5. To assess the effect of SOBI003 on Quality of Life
6. To assess the effect of SOBI003 on language
7. To assess the effect of SOBI003 on motor function
8. To assess the effect of SOBI003 on sleep pattern

9. To assess the immunogenicity of SOBI003
10. To characterize steady-state pharmacokinetics (PK) of SOBI003 by the use of non-compartmental analysis (NCA)

### 6.3.1 Secondary endpoints

The endpoints relating to the 1st secondary objective are:

- Change from baseline at Weeks 52 and 104 in adaptive behavior age-equivalence score (AEq) as assessed by Vineland Adaptive Behavior Scales, Second edition (VABS-II)

The endpoints relating to the 2nd secondary objective are:

- Change from baseline at Weeks 52 and 104 in serum HS
- Change from baseline at Weeks 52 and 104 in urine HS

The endpoints relating to the 3rd secondary objective are:

- Change from baseline at Weeks 52 and 104 in gray matter volume as assessed by brain volumetric MRI
- Change from baseline at Weeks 52 and 104 in compound ventricular volume as assessed by brain volumetric MRI
- Change from baseline at Weeks 52 and 104 in fractional anisotropy (FA) and mean diffusivity (MD) of corpus callosum as assessed by diffusion tensor imaging MRI
- Change from baseline at Weeks 52 and 104 in FA and MD of cerebral white matter as assessed by diffusion tensor imaging MRI
- Change from baseline at Weeks 52 and 104 in cerebral white matter as assessed by susceptibility weighting imaging (SWI) MRI
- Change from baseline at Weeks 52 and 104 in basal ganglia as assessed by SWI MRI

The endpoints relating to the 4th secondary objective are:

- Change from baseline at Weeks 52 and 104 in liver volume as assessed by abdominal MRI
- Change from baseline at Weeks 52 and 104 in spleen volume as assessed by abdominal MRI

The endpoints relating to the 5th secondary objective are:

- Change from baseline at Weeks 52 and 104 in Pediatric Quality of Life inventory (PedsQL) total score and PedsQL™ Family Impact Module total score

The endpoints relating to the 6th secondary objective are:

- Change from baseline at Weeks 52 and 104 in expressive language AEq score as assessed by the BSID-III language subtests or the KABC-II Expressive Vocabulary subtest, and the VABS-II communication domain

- Change from baseline at Weeks 52 and 104 in receptive language AEq score as assessed by the BSID-III language subtests or the KABC-II Expressive Vocabulary subtest, and the VABS-II communication domain

The endpoints relating to the 7th secondary objective are:

- Change from baseline at Weeks 52 and 104 in gross motor function AEq score as assessed by the BSID-III motor subtests and the VABS-II
- Change from baseline at Weeks 52 and 104 in fine motor function AEq score as assessed by the BSID-III motor subtest and the VABS-II

The endpoints relating to the 8th secondary objective are:

- Change from baseline at Weeks 52 and 104 in sleep pattern as assessed by the Children's Sleep Habits Questionnaire (CSHQ) score
- Change from baseline at Weeks 52 and 104 in sleep-related variables as assessed by actigraphy (including total sleep time, total day- and night time sleep duration, sleep latency, sleep efficiency, number of nocturnal awakenings, and wake after sleep onset)

The endpoints relating to the 9th secondary objective are:

- Occurrence of ADAs against SOBI003 in serum at Weeks 38, 52, 78 and 104, and adjacent to dose adjustments (seroconversion rate, time to seroconversion, transient/persistent). For patients with confirmed ADA positive serum samples, the following additional endpoints apply; ADA titers and IgG subclasses in serum, and presence of neutralizing antibodies (NAb) in serum.
- Occurrence of ADAs against SOBI003 in CSF at Weeks 52 and 104 (conversion rate, time to occurrence, transient/persistent). For patients with confirmed ADA positive CSF samples, the following additional endpoints apply: ADA titers and presence of NAb in CSF.

The endpoints relating to the 10th secondary objective are:

- Serum SOBI003 multiple-dose PK parameters at Weeks 38, 52, 78 and 104, and adjacent to dose adjustments;  $t_{\text{End of inf}}$ ,  $C_{\text{End of inf}}$ ,  $C_{\text{Pre-dose}}$ ,  $AUC_{0-168h}$ ,  $CL$
- SOBI003 concentrations in CSF at Weeks 52 and 104.

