### **7.5.3.5 Language**

Expressive and receptive language are assessed at Weeks 52 and 104, and during Early Termination, by the BSID-III language module and the VABS-II communication domain. In addition, written language is assessed by the VABS-II communication domain.

For those patients taking the KABC-II for cognitive assessment, the Expressive Vocabulary from the KABC-II is applied to assess language development.

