14.7 Other efficacy endpoints

Endpoints relating to the neurocognition, liver and spleen volume, QoL, language, motor function and sleep pattern are summarized using descriptive statistics.

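### For children tested on KABC-II alone, the direct-test part of the receptive-language endpoint is the expressive score under a second name

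*Protocol*

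**What the plan says.** Protocol Section 6.3.1 gives two endpoints for the 6th secondary objective, each a change from the FIH baseline at Weeks 52 and 104.

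- The first is "expressive language AEq score as assessed by the BSID-III language subtests or the KABC-II Expressive Vocabulary subtest, and the VABS-II communication domain".
- The second is "receptive language AEq score as assessed by the BSID-III language subtests or the KABC-II Expressive Vocabulary subtest". Its sentence also ends with VABS-II, so the full tail in both endpoints is "KABC-II Expressive Vocabulary subtest, and the VABS-II communication domain".

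The two definitions differ only in the word that names the construct. The protocol synopsis and SAP Section 3.5.4 repeat them unchanged.

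Protocol Section 7.5.3.5 is worded differently. It says expressive and receptive language are assessed "by the BSID-III language module and the VABS-II communication domain", and that VABS-II communication also covers written language. It then adds: "For those patients taking the KABC-II for cognitive assessment, the Expressive Vocabulary from the KABC-II is applied to assess language development". It does not say that this subtest measures receptive language.

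On analysis, SAP Section 14.7 says only: "Endpoints relating to the neurocognition, liver and spleen volume, QoL, language, motor function and sleep pattern are summarized using descriptive statistics". No rule separates receptive from expressive scores for children on KABC-II.

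**The concern.** An endpoint called receptive should draw on a receptive measure. By its name, Expressive Vocabulary is an expressive test; the documents do not describe its content. If the endpoint is programmed as written, a child on KABC-II alone contributes one number twice, once under each label. A table of receptive change would then mix BSID-III receptive scores with KABC-II expressive scores, and nothing in the plan would alert the reader.

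A change of test adds a further problem. A baseline on BSID-III receptive language followed by a later score on Expressive Vocabulary yields a difference between two constructs. At stake is whether one of the two prespecified language endpoints can be interpreted for these children.

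**Working it through.** The plan states no figure to reproduce. The check compares passages and adds a little algebra.

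**1. Is a receptive KABC-II test named anywhere?** The synopsis, Protocol 6.3.1 and SAP 3.5.4 name only Expressive Vocabulary. So does Protocol 7.5.3.5, for language development in general. No receptive KABC-II test appears, so no other passage repairs the endpoint.

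**2. Which children are affected?** Protocol Table 11 and SAP Table 2 allocate the test as follows:

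| Age | VABS-II age-equivalence | Test | Direct receptive score available? |
|---|---|---|---|
| under 42 months | any | BSID-III | yes, BSID-III |
| 42 months or more | below 36 months | BSID-III | yes, BSID-III |
| 42 months or more | 36 to 42 months | both | yes, BSID-III |
| 42 months or more | above 42 months | KABC-II | no |

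Only the last row is without a direct receptive score.

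**3. Can a child change test?** The passages point in different directions.

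- Against: Protocol 7.5.3.1 and SAP 9.3 fix the choice at the FIH baseline and say the same test should be used in the extension.
- For: Protocol 7.5.1.5.2 and 7.5.1.6.2 choose the test at Weeks 52 and 104 from the VABS-II score, and list language among the things tested.
- For, but limited: Protocol 7.5.3.1 lets KABC-II take over when a calibration confirms that a child has outgrown BSID-III. This is written for DQ, though Section 7.5.3.5 ties the language test to the cognitive test.

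A change of test is restricted but not excluded.

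**4. What is the error in a change score?** Let R and E be a child's receptive and expressive age-equivalents on a common scale, with subscript 0 for baseline and t for follow-up. True receptive change is R_t − R_0.

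- KABC-II at both times: the score is E_t − E_0 = (R_t − R_0) − [(R_t − E_t) − (R_0 − E_0)]. The error is the change in the receptive-expressive gap. It is zero if the gap is stable.
- BSID-III, then KABC-II: the score is E_t − R_0 = (R_t − R_0) − (R_t − E_t). The error is the whole gap at follow-up.

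With 9 to 12 patients planned, and all contributing, one child who changes test moves the mean by 1/12 to 1/9 of that child's gap. The documents give no gap and no count, so the calculation stops there.

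**5. Is KABC-II alone likely to be common?** This is only a rough guide, using cognitive DQ as a stand-in for the VABS-II criterion and the means in the sample-size section. At the natural-history mean baseline DQ of 58.9, an age-equivalent above 42 months needs an age above 42 / 0.589 = 71.3 months. With the planning decline of 9.8, DQ at Week 104 is 58.9 − 9.8 = 49.1. The age then needed is 42 / 0.491 = 85.5 months, or a baseline age of 85.5 − 24 = 61.5 months. Individual children will differ, so this does not show that there are none.

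**The case against.** The strongest case on the other side is that receptive language is still assessed. VABS-II is part of both endpoints, and Protocol 7.5.3.5 assigns receptive language to BSID-III and VABS-II without naming KABC-II as a receptive measure. On that view the endpoint lists merely carried the expressive wording forward. This stands as a limit on scope. A reader might infer that receptive language goes unmeasured, or that the endpoint is wrong for every child who takes KABC-II. The documents support neither: VABS-II is completed for all, and children in the 36 to 42 month band also take BSID-III. Nor does Section 7.5.3.5 correct the endpoint lists; it conflicts with them, and the SAP keeps the endpoint wording.

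A second objection is that changing test is discouraged and that a stable gap cancels for children on KABC-II throughout. Both parts stand. A reader might infer a sizeable spurious receptive loss, since Protocol 5.1.1 calls speech delay the most prominent finding of the first disease phase. That passage gives no expressive-receptive difference, and nothing supports any particular number of children changing test.

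A third objection is that VABS-II may not fully fill the gap, because both endpoints cite the whole communication domain. Protocol 7.5.3.2 refers to subdomain age-equivalents, so a receptive part should be obtainable, but the endpoint does not select it. The fix below does.

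**Conclusion.** The point holds for the direct-test component in children tested on KABC-II alone. For them the receptive endpoint repeats the expressive score and adds no receptive information; what remains is caregiver report. A change from BSID-III to KABC-II would also make the direct-test change a difference between two constructs.

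The size of the error cannot be derived from the documents, and any figure in months would be an assumption. The consequence is modest: language is summarized descriptively, lies outside the hierarchical procedure of SAP Section 14.3, and carries no test or sample-size claim. The conclusion assumes that Expressive Vocabulary is what its name says and that the BSID-III language tests yield a separate receptive score. It should still be corrected, because this is a wrong endpoint rule and not merely missing detail, and a study report would repeat the label.

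**What to change.** - Remove KABC-II Expressive Vocabulary from the receptive endpoint in the synopsis, Protocol 6.3.1 and SAP 3.5.4. Keep it for the expressive endpoint only.
- For children on KABC-II alone, define receptive change by the receptive part of VABS-II communication. It is collected at Weeks 52 and 104 and at Early Termination, with the FIH baseline.
- Report direct-test receptive change only for children with BSID-III receptive scores at both time points, and show how many contribute.
- Align Protocol 7.5.3.5 by stating that Expressive Vocabulary serves expressive language.

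The motor endpoints offer a precedent: they rest on BSID-III and VABS-II, with no KABC-II subtest.

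The cost is wording in three endpoint lists and one assessment section, with no new test or visit. The downside is that fewer children have a direct-test receptive score, and the receptive measure for children on KABC-II alone is caregiver-reported.
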